5.6 General Concomitant Medication and Supportive Care Guidelines

Participants who have developed flu-like symptoms that are controlled with acetaminophen or non-steroidal anti-inflammatory drugs during previous treatments may be pre-treated with acetaminophen (650 mg PO) or ibuprofen (400-600mg PO) as per the investigator's discretion.

Participants may not receive any non-oncology vaccine therapy (with the exception of vaccination against the SARS-CoV-2 virus for the prevention of COVID-19 disease) during the 4-week period to first dose of Nivolumab and until at least 8 weeks after the last dose of Neoantigen Vaccine administration.

Given the severity of the COVID-19 pandemic, vaccination specifically against the SARS-CoV-2 virus for the prevention of COVID-19 is ALLOWED in this study.

Investigators may prescribe all other concomitant medications or treatments deemed necessary to provide adequate patient care.

Management of more serious toxicities will be directed by a study investigator following discussion with study PI and will be in accordance with standard of care clinical practice.

5.7 Duration of Therapy / Criteria for Taking a Participant Off Protocol Therapy

Duration of therapy will depend on tolerability of the immunizations and evidence of disease recurrence or progression as judged by the treating investigator. In the absence of treatment delays due to adverse events, treatment will be given for two years in patients with unresectable melanoma and for one year (13 doses) for participants with stage III/B/C/D or IV completely resected melanoma, respectively, or until one of the following criteria applies:

- Disease progression or recurrence, if it is deemed by the treating investigator to be in the best interest of the participant to discontinue study treatment. If there is clinical or radiographic disease progression or recurrence prior to initiation of vaccine at week 12 or at the week 12 scan, treatment as per protocol (Nivolumab plus NeoVax + Montanide + local Ipilimumab) should be given unless deemed not in the best interest of the patient by the investigator.
- Intercurrent illness that prevents further administration of treatment
- Unacceptable adverse event(s)
- Participant demonstrates an inability or unwillingness to comply with protocol requirements
- Participant decides to withdraw from the study, or
- General or specific changes in the participant's condition which render the participant unacceptable for further treatment in the opinion of the treating investigator.

Participants will be removed from the protocol therapy when any of these criteria apply. The reason for removal from protocol therapy, and the date the participant was removed, must be documented in the case report form (CRF). Alternative care options will be discussed with the participant.

When a participant is removed from protocol therapy and/or is off of the study, the relevant Off-Treatment/Off-Study information will be updated in OnCore.

In the event of unusual or life-threatening complications, participating investigators must immediately notify the Principal Investigator, [name], PhD at DFCI [REDACTED]

5.8 Duration of Follow Up

Participants removed from study for unacceptable adverse events will be followed until resolution or stabilization of the adverse event. All participants will be followed until resolution or stabilization of any serious adverse events occurring during treatment or starting within 100 days of last study drug.

Accrual duration is expected to be around 2 years. The overall study duration will be approximately 6 years.

Active Follow-Up: Participants removed from active study treatment will enter active follow-up and will be followed at the following schedule until initiation of a new therapy for progressive disease, withdrawal of consent, or death (whichever comes first):

- At least every 3 months (+/- 2 weeks) for the first 2 years after initiation of study therapy
- At least every 4 months (+/- 2 weeks) for the third year after study therapy initiation
- And at least every 6 months (+/- 4 weeks) thereafter, until 5 years have passed since study therapy initiation

NOTE: When progression is noted during follow-up, the respective measurements documenting progression will be recorded on the appropriate CRF.

Long-Term Follow-Up: Participants removed from active follow-up for progression/initiation of a new therapy will enter long-term follow-up, where they will be followed via medical record review until death for survival. All patients will be followed for survival. Updates to the CRFs are to be made roughly every six months.

5.9 Nivolumab treatment beyond progression

Accumulating evidence indicates a minority of subjects with unresectable melanoma treated with immunotherapy may derive clinical benefit despite initial evidence of progressive disease (PD). Subjects with unresectable stage III/C/D or IV melanoma who show initial evidence of progression (as defined by modified RECIST 1.1) after or during vaccination will be permitted to continue or resume treatment with Nivolumab if documented, as long as they meet all of the following criteria:

- Investigator-assessed clinical benefit
- Subject has tolerated prior Nivolumab
- Stable or improved performance status
- Treatment beyond progression will not delay an intervention to prevent imminent serious complications of disease progression (e.g, CNS metastases)

Subject will be required to sign written informed consent prior to receiving additional Nivolumab treatment, using an ICF describing any reasonably foreseeable risks or discomforts and other alternative treatment options. The assessment of clinical benefit should take into account whether the subject is clinically deteriorating and unlikely to receive further benefit from continued Nivolumab treatment.

A radiographic tumor assessment must be performed 4 to 8 weeks after the assessment documenting initial PD. Subjects must discontinue study treatment upon evidence of further progression on the next scheduled tumor assessment, defined as an additional 10% or greater increase in tumor burden from the time of initial PD (including all target lesions and new measurable lesions). If further progression is not documented on this next tumor assessment, then study treatment may continue until there is evidence of further progression on any subsequent tumor assessment.

New lesions are considered measurable at the time of initial PD documented if the longest diameter is at least 10 mm (except for pathological lymph nodes, which must have a short axis of at least 15 mm). Any new lesion considered non-measurable at the time of initial PD may become measurable and therefore included in the tumor burden measurement if the longest diameter increases to at least 10 mm (except for pathological lymph nodes, which must have an increase in short axis to at least 15 mm).

For statistical analyses that include the investigator-assessed progression date, subjects who continue Nivolumab treatment beyond initial investigator-assessed progression, as defined by modified RECIST 1.1, will be considered to have investigator-assessed progressive disease at the time of the initial progression event.

5.10 Criteria for Taking a Participant Off Study

Participants will be removed from study when any of the following criteria apply:

- Dose-limiting toxicity (DLT) as defined in protocol section 5.5
- Grade 3 or greater skin toxicity (ulcer)
- Lost to follow-up
- Failure to produce an adequate supply of acceptable vaccine
- Withdrawal of consent for data submission
- Death

The reason for taking a participant off study, and the date the participant was removed, must be documented in the case report form (CRF). In addition, the study team will ensure Off Treatment/Off Study information is updated in OnCore in accordance with DF/HCC policy REGIST-101.

In the event of unusual or life-threatening complications, participating investigators must immediately notify the Principal Investigator, [name], PhD at DFCI [REDACTED]
[REDACTED].

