6.3.2 NeoVax plus Montanide

6.3.2.1 If a participant develops grade 3 toxicity attributable to the vaccine, additional treatment will be withheld until the toxicity has resolved or improved to grade 1. If the toxicity constitutes a DLT as defined in 5.6, the participant will be removed from the study. If the toxicity does not fulfill the criteria of a DLT, the next vaccine administration may be delayed for a maximum duration of 14 days. If vaccine dosing has to be delayed more than 2 times because of an attributable toxicity that is not considered a DLT, the participant will be removed from the study

6.3.2.2 If a participant develops grade 4 toxicity attributable to the vaccine s/he will be removed from treatment

6.3.2.3 If two or more grade 4 or greater toxicities attributable to the vaccine are observed, the trial will be suspended to investigate the causes of these (unexpected) toxicities

6.3.2.4 Vaccine dosing may be delayed in the event of unrelated adverse events if it is felt to be in the medical best interest of the patient following discussion by the treating investigator with the study Principal Investigator or designee. Vaccine dosing may be resumed once the treating investigator deems it is medically safe to do so following discussion with the study Principal Investigator or designee as long as the participant has not developed progressive disease

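### A DLT takes a participant off study in Sections 5.10 and 6.3.2.1, while Section 5.8 follows everyone off treatment; read literally, the conflict can cost the progression/recurrence count its most toxic patients

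*Protocol*

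**What the plan says.** The protocol separates two statuses. Section 5.7 is the off-therapy list. It includes unacceptable adverse events and closes with "Participants will be removed from the protocol therapy when any of these criteria apply". Section 5.10 is the off-study list and opens with "Participants will be removed from study when any of the following criteria apply". Its first entry is "Dose-limiting toxicity (DLT) as defined in protocol section 5.5". Grade 3 or greater skin toxicity and "Failure to produce an adequate supply of acceptable vaccine" are also on it, beside loss to follow-up, withdrawal of consent for data submission, and death.

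Section 6.3.2.1, on grade 3 toxicity attributable to the vaccine, says the same of a DLT: "If the toxicity constitutes a DLT as defined in 5.6, the participant will be removed from the study". (The DLT definition is in 5.5, not 5.6.) The next item, 6.3.2.2, uses the other status: "If a participant develops grade 4 toxicity attributable to the vaccine s/he will be removed from treatment".

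Section 5.8 sets the follow-up: "Participants removed from active study treatment will enter active follow-up and will be followed at the following schedule". That schedule ends at new therapy for progressive disease, consent withdrawal or death. It adds "All patients will be followed for survival". For participants removed from study for unacceptable adverse events, however, the only follow-up it names is of the event itself, to resolution or stabilization.

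The SAP (Statistical Analyses, Secondary Endpoints) counts patients with progression or recurrence. It has no rule for a patient who leaves the study at a DLT.

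**The concern.** A site could justify either of two actions for a patient with a DLT: stop treatment and continue the Section 5.8 schedule, or close the patient out under 5.10. Under the second, scans stop because of toxicity, so the missing outcomes are not a random subset. Progression/recurrence is a secondary objective (Protocol 1.3) and a SAP secondary endpoint. A progression that nobody looks for is not counted, so a count over the whole cohort would tend to be too low. In a cohort of five, each such patient matters.

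**Working it through.** **1. The sections side by side.**

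| Section | Trigger | Consequence stated |
|---|---|---|
| 5.7 | Unacceptable adverse event | Off protocol therapy |
| 5.8 | Off active treatment | Active follow-up to new therapy, consent withdrawal or death; survival for all |
| 5.8 | Off study for unacceptable adverse event | Event followed to resolution or stabilization |
| 5.10 | DLT; grade 3 or greater skin toxicity | Off study |
| 6.3.2.1 | Vaccine-attributable grade 3 toxicity that is a DLT | Off study |
| 6.3.2.2 | Vaccine-attributable grade 4 toxicity | Off treatment |

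A related grade 4 toxicity inside the window is generally a DLT under 5.5. The same event can therefore be off study by 5.10 and off treatment by 6.3.2.2.

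**2. Timing.** Vaccination starts at week 12. The DLT window in 5.5 is 42 days, so it ends at week 12 + 6 = 18 (week 19 under the 7-week window used in 5.4.1 and 13.1). The study calendar places staging scans at weeks 12 and 24, then every 12 weeks. On that schedule, a patient taken off study within the window has had no scheduled scan after the first vaccination. This assumes no delay in vaccination and uses the calendar; Section 11.1 gives an 8-week interval, which disagrees with both the calendar and the opening of Section 11.

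**3. The plan's own figures.** P(0 or 1 DLT in 5) = (1−p)^5 + 5p(1−p)^4.
- p = 0.10: 0.590 + 0.328 = 0.919 (stated 92%)
- p = 0.20: 0.328 + 0.410 = 0.737 (stated 74%)
- p = 0.30: 0.168 + 0.360 = 0.528 (stated 53%)

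The largest 90% exact (Clopper-Pearson) interval width for n = 15 is 0.456, which matches the stated limit of 0.46. Nothing in the plan's arithmetic is overturned.

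**4. How often a cohort of five would be exposed.** The DLT rates are assumptions. P(at least one DLT in 5) = 1 − (1−p)^5.
- p = 0.10: 1 − 0.590 = 0.410 (41%)
- p = 0.20: 1 − 0.328 = 0.672 (67%)
- p = 0.30: 1 − 0.168 = 0.832 (83%)

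The decision rule lets a cohort pass with one DLT, so the problem is not confined to doses that fail.

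**5. What one lost patient does.** One of five is 20%. If x progressions are seen in the other four, the count reads x/5, while the full-follow-up value is either x/5 or (x+1)/5. The error is thus zero or 20 percentage points, always downward. For x = 1, the count gives 1/5 = 20%, the four followed patients alone give 1/4 = 25%, and the true value is 20% or 2/5 = 40%. The largest 90% exact interval width rises from 0.734 (n = 5) to 0.805 (n = 4) if the lost patient is dropped.

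**6. The protocol as designed.** A declared MTD with a completed expansion allows up to 1 of 5 plus 3 of 10, or 4 of 15, with a DLT. If all four are lost and 4 progressions are seen in the other 11, the followed-only rate is 4/11 = 36%, and the possible range is 4/15 = 27% to 8/15 = 53%. The SAP says expansion never opened, so step 5 describes the trial as run.

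**The case against.** The strongest reply is that Section 5.10 never says follow-up stops. It names withdrawal of consent for data submission as its own entry, and only that entry ends data submission by its terms. What off study means in practice is tied to an institutional policy that is not in the documents. The protocol also uses the two statuses loosely: unacceptable adverse events are an off-therapy reason in 5.7, yet 5.8 speaks of participants taken off study for them. A patient with a DLT is also off active treatment, so 5.8 can be read as keeping that patient in follow-up, in which case nothing is lost. This stands. The documents support a conflict that permits loss of follow-up; they do not establish that loss occurs.

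Three stronger inferences are tempting and do not hold.

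- **Late toxicity goes uncaptured.** Section 5.8 follows adverse events leading to removal until resolution or stabilization, and follows serious events starting within 100 days of the last study drug. Sections 7.2.1 and 7.5 set 100-day collection and reporting periods from the end of dosing, not from study status.
- **The primary endpoint is compromised.** The DLT is recorded before the patient leaves, so the DLT rate is unchanged.
- **A survival endpoint is damaged.** Survival is defined in 11.1.6 and has data fields in the SAP, but it is neither a listed objective nor a SAP endpoint with an analysis. The SAP's response denominator is already every patient in the cohort.

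Vaccine-supply failure differs from the toxicity entries. A participant who received nivolumab but no vaccine is evaluable for toxicity under 5.4.3 but not for tumor response, so a blanket instruction to keep such patients in every analysis would contradict that section.

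**Conclusion.** The inconsistency is real and worth correcting. Sections 5.10 and 6.3.2.1 say off study for a DLT, 6.3.2.2 says off treatment for grade 4 vaccine toxicity, and 5.8 follows patients off treatment without a DLT exception. The exposed endpoint is the progression/recurrence count, with a probable downward bias of up to 20 percentage points per lost patient in a cohort of five. The 41%, 67% and 83% figures rest on assumed DLT rates and give the chance that a DLT occurs, not the chance that an outcome is lost. The documents do not say whether any DLT occurred. The conclusion also depends on a literal reading of 5.10 and, for the missed week 24 scan, on vaccination starting on schedule.

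**What to change.** Reconcile Sections 5.7, 5.8, 5.10 and 6.3.2 on follow-up status only, leaving every treatment-discontinuation rule as it is:

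1. State that a DLT or grade 3 or greater skin toxicity does not by itself end the Section 5.8 progression and survival follow-up.
2. Make 6.3.2.1 and 6.3.2.2 consistent with that statement, and correct the cross-reference to the DLT definition.
3. In the SAP, state that these patients stay in the progression/recurrence denominator, and report the number whose follow-up is incomplete.
4. State that participants with vaccine-supply failure who received nivolumab but no vaccine stay in the toxicity-evaluable set under 5.4.3 and are not in the response analysis.

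The cost is a wording amendment and a few sentences in the SAP. No visits are added, because 5.8 already contains the schedule. The change can still matter after accrual closed: first enrolment was expected by September 2020 and active follow-up runs to five years from the start of therapy, that is, to about September 2025 at the earliest for a patient who completes it, beyond the SAP date of November 2023.

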6. EXPECTED TOXICITIES AND DOSING DELAYS/DOSE MODIFICATIONS

Dose delays and modifications will be made as indicated in the following table(s). The descriptions and grading scales found in the revised NCI Common Terminology Criteria for Adverse Events (CTCAE) version 5.0 will be utilized for dose delays and dose modifications. A copy of the CTCAE version 5.0 can be downloaded from the CTEP website http://ctep.cancer.gov/protocolDevelopment/electronic_applications/ctc.htm.

If possible, symptoms should be managed as needed. In the case of toxicity, appropriate medical treatment should be used.

All adverse events experienced by participants will be collected from the time of the first dose of study treatment (first Nivolumab administration), through the study and until the final study visit. Participants continuing to experience toxicity at the end of treatment visit may be contacted for additional assessments until the toxicity has resolved or is deemed irreversible.

6.1 Anticipated Toxicities

A list of the adverse events and potential risks associated with the agents administered in this study appears on section 7.1 and will determine whether dose delays and modifications will be made or whether the event requires expedited reporting **in addition** to routine reporting. If one drug is held due to an AE all the 3 drugs will be held until original AE is resolved.

6.2 Toxicity Management

If treatment needs to be held because of toxicity, all study drug will be held until resolution of the adverse event.

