6.3 Dose Modifications/Delays

6.3.1 Nivolumab

Dose Modifications

Dose reductions or dose escalations are not permitted.

Dose Delay Criteria

Because of the potential for clinically meaningful Nivolumab-related AEs requiring early recognition and prompt intervention, management algorithms have been developed for suspected AEs of selected categories (listed in Appendix B).

- Gastrointestinal
- Renal
- Pulmonary
- Hepatic
- Endocrinopathies
- Skin
- Neurological

Dose delay criteria apply for all drug-related adverse events (regardless of whether or not the event is attributed to Nivolumab). All study drugs must be delayed until treatment can resume.

Dose delay criteria apply for all drug-related AEs. Nivolumab must be delayed until treatment can resume

Nivolumab administration should be delayed for the following:

Any Grade ≥ 2 non-skin, drug-related AE, with the following exceptions:

- Grade 2 drug-related fatigue or laboratory abnormalities do not require a treatment delay
- Any Grade 3 skin, drug-related AE

Any Grade 3 drug-related laboratory abnormality, with the following exceptions for lymphopenia, leukopenia, AST, ALT, total bilirubin, or asymptomatic amylase or lipase:

- Grade 3 lymphopenia or leukopenia does not require dose delay.
- If a subject has a baseline AST, ALT, or total bilirubin that is within normal limits, delay dosing for drug-related Grade ≥ 2 toxicity.
- If a subject has baseline AST, ALT, or total bilirubin within the Grade 1 toxicity range, delay dosing for drug-related Grade ≥ 3 toxicity.
- Asymptomatic amylase or lipase do not require a treatment delay

Any AE, laboratory abnormality, or intercurrent illness which, in the judgment of the investigator, warrants delaying the dose of study medication.

Criteria to Resume Treatment

Subjects may resume treatment with Nivolumab when the drug-related AE(s) resolve to Grade ≤1 or baseline value, with the following exceptions:

- Subjects may resume treatment in the presence of Grade 2 fatigue
- Subjects who have not experienced a Grade 3 drug-related skin AE may resume treatment in the presence of Grade 2 skin toxicity
- Subjects with baseline Grade 1 AST/ALT or total bilirubin who require dose delays for reasons other than a 2-grade shift in AST/ALT or total bilirubin may resume treatment in the presence of Grade 2 AST/ALT OR total bilirubin

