6.4 Criteria to Resume Treatment

Subjects may resume treatment with Ipilimumab and NeoVax plus Montanide when the drug-related AE(s) resolve to Grade \leq 1 or baseline value, with the following exceptions:

- Subjects may resume treatment in the presence of Grade 2 fatigue
- Subjects who have not experienced a Grade 3 drug-related skin AE may resume treatment in the presence of Grade 2 skin toxicity
- Subjects with baseline Grade 1 AST/ALT or total bilirubin who require dose delays for reasons other than a 2-grade shift in AST/ALT or total bilirubin may resume treatment in the presence of Grade 2 AST/ALT OR total bilirubin

- Subjects with combined Grade 2 AST/ALT AND total bilirubin values meeting discontinuation parameters should have treatment permanently discontinued
- Drug-related pulmonary toxicity, diarrhea, or colitis, must have resolved to baseline before treatment is resumed
- Drug-related endocrinopathies adequately controlled with only physiologic hormone replacement may resume treatment

If the criteria to resume treatment are met, the subject should restart treatment at the next scheduled timepoint per protocol. However, if the treatment is delayed past the next scheduled timepoint per protocol, the next scheduled timepoint will be delayed until dosing resumes.

If treatment is delayed > 6 weeks, the subject must be permanently discontinued from study therapy, except as specified in discontinuation section.

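### The protocol gives conflicting rules for when a toxicity hold ends and, for some events, when it starts, so vaccinations given and DLT observation can depend on the section followed

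*Protocol*

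**What the plan says.** **End of a hold.** Protocol Section 6.2 requires that "all study drug will be held until resolution of the adverse event". Section 6.1 is similar: "If one drug is held due to an AE all the 3 drugs will be held until original AE is resolved". Neither names a grade or an exception, and neither points to another section for the restart condition.

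Section 6.4 covers ipilimumab and the vaccine: "Subjects may resume treatment with Ipilimumab and NeoVax plus Montanide when the drug-related AE(s) resolve to Grade" 1 or lower, or to baseline. Exceptions follow, among them "Drug-related endocrinopathies adequately controlled with only physiologic hormone replacement may resume treatment". Section 6.3.1 has the same list for nivolumab. Both sections make a delay beyond 6 weeks a permanent discontinuation, subject to the exceptions in the discontinuation criteria.

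Section 6.3.2.1 has its own rule for vaccine toxicity: "additional treatment will be withheld until the toxicity has resolved or improved to grade 1". It lists no exceptions. If the toxicity is not a DLT, the next vaccination may be delayed by at most 14 days, and more than two such delays remove the participant.

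**Start of a hold.** Section 6.3.1 applies its delay criteria to drug-related events whether or not they are attributed to nivolumab, and states: "All study drugs must be delayed until treatment can resume". The trigger is grade 2 or higher for non-skin events. Grade 2 fatigue and grade 2 laboratory abnormalities are excepted, although grade 2 AST, ALT or bilirubin counts when baseline was normal. Section 6.3.3.2 repeats this trigger for ipilimumab. Section 6.3.2.1 begins at a different grade: "If a participant develops grade 3 toxicity attributable to the vaccine". Section 6.2.2.2 allows vaccination to continue, under conditions, after a grade 1 or 2 allergic reaction.

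**The concern.** An investigator with a patient on hold can find three different restart conditions and two different starting grades, all in current text, with no statement of which section prevails. In a small escalation study this is more than untidy drafting. Section 5.4.3 requires at least two vaccinations for a patient to complete DLT observation, and Section 5.5 lengthens the DLT window by the duration of any delay for a non-DLT toxicity. The hold rule therefore feeds into the primary endpoint: who has been fully observed, and for how long.

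**Working it through.** No sample size or rate enters this point, so the check is mainly a comparison of text.

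| Section | Applies to | Hold starts | Hold ends | Longest delay |
|---|---|---|---|---|
| 6.1, 6.2 | all study drugs | when any drug is held | event resolved | not stated |
| 6.3.1 | nivolumab; delay extended to all study drugs | grade 2 or higher, non-skin, with exceptions; grade 3 skin | grade 1 or lower, baseline, or listed exception | 6 weeks, with exceptions |
| 6.3.3.2, 6.4 | ipilimumab (start and restart); vaccine (restart) | same trigger as 6.3.1 | same as 6.3.1 | 6 weeks, with exceptions |
| 6.3.2.1 | vaccine | grade 3 attributed to vaccine | resolved or grade 1 | 14 days if not a DLT |
| 6.2.2.2 | vaccine, allergic reactions | grade 1-2 may continue | not applicable | not stated |

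**Case 1, end of hold.** Take a grade 2 drug-related endocrinopathy after the week 12 vaccination, controlled on replacement but still needing it when the week 15 dose is due. Sections 6.3.1 and 6.3.3.2 start a hold. Section 6.4 then permits restart, so the second vaccination can be given. Sections 6.1 and 6.2, read as written, keep the hold in place because the event has not resolved. On the first reading the patient can reach the two vaccinations required by 5.4.3. On the second, not while the hold lasts.

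**Case 2, length of hold.** Take a grade 3 vaccine-related rash that falls to grade 2 within 14 days, which 5.5 excludes from DLT, and then stays at grade 2. The rash itself caused the hold under both 6.3.1 and 6.3.2.1. Section 6.3.2.1 caps the delay of the next vaccination at 14 days and does not say what follows if grade 1 has not been reached. Section 6.4 allows up to 6 weeks (42 days). Section 5.5 adds the delay to a 42-day window:

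- under the 14-day cap: 42 + 14 = 56 days
- under the 6-week limit: 42 + 42 = 84 days
- difference: 84 − 56 = 28 days

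I use the 42 days of Section 5.5. Section 13.1 and the SAP also speak of 7 weeks, which is a separate matter.

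**Case 3, start of hold.** Take a grade 2 non-skin vaccine-related event, neither fatigue nor a laboratory abnormality, present when a vaccination is due. Section 6.3.1 delays all study drugs. Section 6.3.2.1 is not triggered. If the event is an allergic reaction, 6.2.2.2 permits continuation. If the event has settled before the visit, there is no practical conflict.

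**Where the conflict does not reach.** The discontinuation criteria in 6.3.1 and 6.5 end treatment for most grade 3 non-skin events lasting more than 7 days. The restart conflict therefore falls mainly on grade 2 events, short grade 3 events and grade 3 skin events.

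**Link to the decision rule.** Escalation turns on 0-1 against 2 or more DLTs in 5 patients (Sections 5.4.1 and 13.1). Neither 5.4.3 nor 13.1 says how a patient with one vaccination and no DLT counts among the five. The SAP's primary analysis is the proportion with a DLT, and no denominator is given for it.

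**The case against.** The strongest reply is that 6.1 and 6.2 exist only to hold the drugs together, and that the sections headed as resume criteria supply the actual condition. The protocol does attach grades to the verb resolve, in 6.4 and again in 5.5. This weakens the contrast between resolution and grade 1, but does not remove it. Section 6.3.2.1 lists resolved and improved to grade 1 as alternatives, so the protocol treats them as different states. A patient still on replacement hormone fits no ordinary sense of resolved. No clause gives the specific section priority.

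It can also be said that 6.3.2.1 never states that vaccination continues at grade 2, so its grade 3 rule could sit on top of a grade 2 hold. That is a fair way to read the sections together, but 6.2.2.2 does expressly permit continuation after grade 2 allergic reactions. The sentence after "All study drugs must be delayed until treatment can resume" restates the delay for nivolumab alone, which might seem to confine the grade 2 trigger to that drug. But 6.3.3.2 repeats the trigger for ipilimumab, and 6.1 carries one drug's hold to all three.

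Two further replies stand in full:

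- **Other restart exceptions.** A reader might count "Subjects may resume treatment in the presence of Grade 2 fatigue" and the grade 2 skin exception as further contradictions. Mostly they are not. Grade 2 fatigue does not itself start a hold, and the skin exception is limited to patients who have not had a grade 3 skin event. Both usually describe an event that coexists with the one that caused the hold.
- **Shifted injection sites.** A reader might cite Section 6.2.2.1, which lets injections move away from a persistent local reaction. It gives no grade and concerns where to inject, so it does not conflict with the hold rules.

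**Conclusion.** The inconsistency is real and moderate in importance. The end of a hold is written three ways. The start is written two ways for a limited set of grade 2 non-skin events. Depending on the section followed, a patient may or may not receive a second vaccination in time to complete DLT observation, and one maximal delay can stretch the window to 56 or to 84 days. This rests on reading the sections as written, with no unstated order of precedence.

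Three stronger inferences are not supported:

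- **Four doses against one.** This needs an event after dose 1 that never resolves. It also needs the 6-week discontinuation rule to be applied while the endocrinopathy exception in the same sections is ignored. It is an extreme case, not the expected effect.
- **A percentage of patients or cohorts affected.** The documents give no rate for such events, so any figure would be invented.
- **A wrong MTD.** Nothing in the documents shows that a hold altered a DLT call or an escalation decision.

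**What to change.** Reconcile Sections 6.1, 6.2, 6.2.2.2, 6.3.1, 6.3.2.1, 6.3.3.2 and 6.4 so that each drug has one start-of-hold rule, one restart rule and one maximum delay. Replace the free-standing wording in 6.1 and 6.2 with a cross-reference to that rule. Which clinical rule applies is for the sponsor to decide.

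The SAP, dated November 2023, says accrual stopped once the MTD was determined, so new wording cannot change holds already made during escalation. The more useful step now is a per-patient listing: each dose withheld or delayed, the reason, the length of the delay, the resulting DLT window, DLT status, and whether the two-vaccination requirement was met. The SAP's toxicity variable list and its Statistical Analyses section contain no such item. The cost is a wording amendment and one listing from dosing records, with no new procedures for patients.
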